Appendix 4: PATCH 3 Job Aid

PATCH3 STUDY LEAD JOB AID

A PATCH3 AUTOMATIC STUDY EXCLUSIONS	
Consumer Language for Enrollment Exclusions 
 These exclusions are automatic during the online enrollment experience in the enrollment portal If indicated exclusion response is selected, it is an automatic exclusion from the study 	Automatic Portal Exclusion
Are you a health care worker scheduled to working an average of 20 hours a week for the next 2 months?	If NO
Are you currently asymptomatic and presume not to have COVID?	If NO
Have you had a fever within the last four days? [yes/ no]	If NO
Do you require hospitalization? [yes/ no]	If YES
Are you able to self-quarantine at home for 14 days? [yes/ no]	If NO
Have you been tested for COVID-19? [yes/ no]	If NO

B AUTOMATIC CLINICAL EXCLUSIONS		
Consumer Language for Enrollment Exclusions 
 These exclusions are automatic during the online enrollment experience in the enrollment portal If “yes” to any, it is an automatic exclusion from the study. 	Automatic Portal Exclusion	
Protocol Language: Allergy to hydroxychloroquine, 4 aminoquinolines, or quinine	Do you have an allergy to hydroxychloroquine (HCQ), aminoquinolines, or quinine? [yes/ no]	X
Protocol Language: Patients with G6PD deficiency	Do you have a G6PD deficiency? [yes/ no]	X
Protocol Language: Pregnant or lactating or positive pregnancy test during pre-medication examination	Are you pregnant? [yes/ no]	X
	Are you breast feeding? [yes/ no]	X
Protocol Language: Receiving any trial treatment drug for 2019-ncov within 14 days prior to screening evaluation (off label, compassionate use or trial related)	Have you been in any other drug trial for COVID-19? [yes/ no]	X
Protocol Language: Patients with serious intercurrent illness that requires active infusional therapy, intense monitoring, or frequent dose adjustments for medication including but not limited to infectious disease, cancer, autoimmune disease, cardiovascular disease.	Are you on any IV or other serious medications, such as chemotherapy? [yes/ no]	X
Protocol Language: Patients who have undergone major abdominal, thoracic, spine or CNS surgery in the last 2 months, or plan to undergo surgery during study participation.	Have you had any surgery in the last two months? [yes/ no]	X
Protocol Language: Patients currently taking digoxin	Do you take the medication, digoxin or lanoxin? [yes/ no]	X

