(From Medication Section)	Have you ever had a seizures? [yes/ no]	X

PATCH 2 & 3 TRIAL

(From Medication Section)	Have you ever had a transplant? [yes/ no]	X
Protocol Language: History or evidence of increased cardiovascular risk including any of the following: 
 Left ventricular ejection fraction (LVEF) < institutional lower limit of normal. Baseline echocardiogram is not required; Current clinically significant uncontrolled arrhythmias. Exception: Subjects with controlled atrial fibrillation; History of acute coronary syndromes (including myocardial infarction and unstable angina), coronary angioplasty, or stenting within 6 months prior to enrollment; Current ≥ Class II congestive heart failure as defined by New York Heart Association. 	Do you have any heart disease such as congestive heart failure, history of heart attack, angina, arrhythmias or atrial fibrillation (also called AFib)? [yes/ no]	X

C STUDY LEAD DECIDED EXCLUSIONS

Consumer Language for Enrollment Exclusions

- These exclusions will be asked prior to the consent call through the study enrollment portal. “Yes” response do not trigger an automatic exclusion.
- “Yes” responses require a live conversation between the prospective participant and the study lead during live consent.
- If a medical consult is needed, then the study lead will conduct a medical consult with study PIs. Track all medical consult language in the study portal.
- Call the prospective study participant back with the final decision (yes or no) on enrollment. If he/she is eligible, then finish study consenting, and trigger tablet + journal shipment

DISEASE EXCLUSIONS

Protocol Language	Study Portal Language		
Eye Disease: Known retinal disease including but not limited to macular degeneration, retinal vein occlusion, visual field defect, diabetic retinopathy	Do you have eye disease? [yes/ no]		
	(if yes) Please describe. [open text]		
	INCLUDED IF:	MEDICAL CONSULTATION IF:	EXCLUSION IF:
	Wears eye glasses		Any eye disease

Protocol Language	Study Portal Language		
Lung Disease: History of interstitial lung disease, severe emphysema or asthma, or chronic pneumonitis unrelated COVID-19.	Do you have lung disease, such as asthma or emphysema? [yes/ no]		
	(if yes) Please describe. [open text]		
	INCLUSION IF:	MEDICAL CONSULTATION IF:	EXCLUSION IF:
	If moderate or controlled	If in question, then medical consult	If severe, then exclude

Protocol Language	Study Portal Language		

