	
 The HCQ Medication Guide opens with: “You have received your medication tablets in this box. These tablets may be a placebo or they may be the active hydroxychloroquine (HCQ) medication. Below is a list of possible side effects from taking active HCQ.”

PATCH3 HEALTH CARE WORKER CROSSOVER KIT

Content	Description
	
CROSSOVER MEDICATION Unblinded Active HCQ - 42 tabs Medication ID: [bottle serial number] Contents: 42 tablets Directions: Take 3 pills in the AM daily for 14 days. No refill. Store at [insert storage instructions from the manufacturer] Caution: New Drug - Limited by Federal (or United States) law to investigational use

	
CROSSOVER GUIDE This guide is to support the health care worker with instructions when crossing over from placebo to HCQ should they qualify.

E FREQUENTLY ASKED QUESTIONS (FAQ)

Type of Question	Question	Response
Study Info	What is the PATCH Study?	PATCH, also known as Prevention and Treatment of COVID-19 with Hydroxychloroquine (HCQ), is a research study that is being conducted by ProHEALTH NY, University of Pennsylvania, and UnitedHealth Group Research & Development to determine if HCQ can be an effective antiviral medication for preventing and treating COVID-19.
Study Info	What will be expected of me if I decide to participate in this study?	A package will be sent to you with either HCQ active or placebo pills. We ask that you take your medication according to the package direction, check your temperature twice daily or report symptoms of fever, record and report any adverse events, and upload this information daily through the study portal at patchstudy.com for the full duration of this study. You'll also be asked to get your swab samples taken at the end of the study.
Study Info	Can anyone join?	The PATCH2 Study is focused on recruiting patients who are: 
 • between the ages of 50-75 years of age • experiencing COVID-19 symptoms such as cough, fever, and/or sore throat • being sent home for a 14-day self-quarantine after being tested for COVID-19

PATCH 2 & 3 TRIAL

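### The PATCH 3 online screen automatically rejects health care workers with no recent fever or no prior COVID-19 test, though the PATCH 3 criteria require neither

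*Combined protocol and SAP*

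**What the plan says.** Appendix 4, part A, sets out the automatic study exclusions for PATCH 3 and gives the rule: "If indicated exclusion response is selected, it is an automatic exclusion from the study". Among its six questions are "Have you had a fever within the last four days? [yes/ no" and "Have you been tested for COVID-19? [yes/ no", and the excluding answer to each is NO. The same table asks "Are you currently asymptomatic and presume not to have COVID", where NO also excludes.

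The PATCH 3 inclusion criteria appear in the Synopsis, in Section 3.1 and in step 2 of the PATCH 3 procedure in Section 4.0. Each describes a currently employed health care worker who has no symptoms, is presumed negative without a confirmatory test, and is scheduled for about 20 hours or more of clinical care a week over the next two months. Testing comes later. Section 8.4 calls for it when influenza-like symptoms appear and, for those still undiagnosed, on Days 61 to 63.

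Step 1 of the PATCH 3 procedure in Section 4.0 is the online eligibility checklist. Section 3.1 also refers to the job aid, under the combined exclusion criteria.

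**The concern.** The screen and the criteria describe different people. PATCH 3 is a prophylaxis study in workers presumed uninfected, yet the printed screen demands a fever in the past four days and a COVID-19 test already taken. It also demands that the applicant be free of symptoms now. Those answers can coexist only in someone whose fever has recently resolved.

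Two things are at stake. The first is accrual: Section 16.1 needs 350 workers, and the screen rejects those with no recent fever or no prior test. The second is who gets in. The primary outcome is COVID-19 infection over two months, and no confirmatory test is done at entry. Selecting workers by recent fever runs against the presumption that the cohort is negative at the start.

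**Working it through.** No plan figure enters this point, so the check sets each row of Appendix 4, part A, against the PATCH 3 criteria and against part A of the PATCH 2 job aid (Appendix 3).

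| Question in Appendix 4, part A | Excluding answer | Basis in the PATCH 3 criteria | Same row in Appendix 3 |
|---|---|---|---|
| Health care worker, about 20 h/week for 2 months | NO | Yes | No |
| No symptoms, presumed free of COVID | NO | Yes | No |
| Fever in past four days | NO | None | Yes |
| Needs hospitalization | YES | Not stated, but consistent with having no symptoms | Yes |
| Able to self-quarantine 14 days | NO | None | Yes |
| Tested for COVID-19 | NO | None | Yes |

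**Source of the rows.** Appendix 3, part A, has five questions. Four of them (fever, hospitalization, self-quarantine, tested) appear in Appendix 4 with the same excluding answers. Only the age question was replaced, by the two PATCH 3 questions at the top of the table. The fever row fits PATCH 2, whose inclusion criterion in Section 3.1 is a self-reported fever within four days before enrolment.

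**Effect on an eligible worker.** Take a worker who answers the other four rows acceptably: health care worker yes, no symptoms yes, hospitalization no, able to self-quarantine yes. The exclusions triggered are:

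| Recent fever | Prior test | Exclusions triggered (of 6) | Outcome |
|---|---|---|---|
| No | No | 2 | Rejected |
| No | Yes | 1 | Rejected |
| Yes | No | 1 | Rejected |
| Yes | Yes | 0 | Passes |

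Only one of the four combinations passes. Of the three statements of the PATCH 3 criteria, 0 require a recent fever and 0 require a prior test. With the two rows deleted, all four combinations trigger 0 of the remaining 4 exclusions.

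**Is there a way back in?** Appendix 4, part C, provides for human review, but only of its own questions. There a yes "response do not trigger an automatic exclusion", and such answers "require a live conversation between the prospective participant and the study lead during live consent". Part A has no such provision, and no other step in the available text recovers an applicant it rejects.

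**Could this be a layout fault?** The table is intact, with one answer per row. The hospitalization row reads YES, so NO is not a value filled down the column.

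**The case against.** The mismatch is hard to dispute. The case on the other side concerns its weight and the remedy.

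- **It is only a job aid.** The criteria in the protocol body agree with each other on this point, and no endpoint, analysis set or error rate is touched. The harm arises only if the portal follows the printed table, and a screen that rejected most applicants might be noticed early. The condition stands and is kept in the conclusion. Still, Section 4.0 makes the online checklist the first step of enrolment, and Appendix 4 says these exclusions operate automatically in the portal, so the table is more than background.
- **The testing row does not fit PATCH 2 cleanly either.** The Synopsis describes PATCH 2 patients as tested, but Section 4.0 puts the PATCH 2 checklist at step 1 and the swab at step 2. This stands. It weakens the contrast between the sub-studies for that row and leaves the PATCH 3 contradiction as it was.
- **The phrase about confirmatory testing is ambiguous.** It may mean that the study runs no baseline test, or that the applicant has not been tested. Neither reading makes a prior test a condition of entry.
- **The fever answer may simply be inverted.** Excluding on YES would suit a symptom-free cohort, and the symptom question does not cover a fever that has already resolved. That is possible, but it would add a criterion found in none of the three statements. On that reading the printed answer is still wrong.
- **The FAQ is weak support.** In Appendix 4 it says "The PATCH2 Study is focused on recruiting patients who are", among other things, "experiencing COVID-19 symptoms such as cough, fever, and/or sore throat". The available text ends soon after, so any PATCH 3 part of the answer may be missing. It is consistent with the rows belonging to PATCH 2 but is not needed for the conclusion.

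**Conclusion.** The concern holds. As printed, Appendix 4, part A, contradicts the PATCH 3 criteria in two of its six rows and rejects an eligible worker who lacks a recent fever, a prior test, or both. It should be fixed, because it is a working rule that gives the wrong result when followed.

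The practical effect depends on the portal having been built from the printed table. The documents do not show this: the enrolment flow figures and the later part of the FAQ are not available. The documents also give no rate of recent fever or prior testing among health care workers, so the number of applicants affected cannot be estimated.

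The self-quarantine row likewise has no counterpart in the PATCH 3 criteria. It asks only about ability, so it is a point to confirm and not a contradiction.

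**What to change.** Delete the fever and prior-test rows from Appendix 4, part A, so that the PATCH 3 screen agrees with Sections 3.1 and 4.0. The existing symptom question continues to cover current symptoms. If the sponsor wants to exclude workers with a recent resolved fever, that should be written into the PATCH 3 criteria in the protocol body first, and the screen should then follow it. Confirm whether the self-quarantine row is meant to apply to PATCH 3. Check the live portal configuration against the corrected table.

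The cost is two deleted rows, one confirmation and a configuration check, with no change to procedures, visits or sample size.
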